7.2.8.2 Disease Progression: Special Considerations for Germ-Cell Cancer

For patients with germ-cell cancer, in addition to a radiologic disease assessment every 84 days (± 7days), biomarker measurement (AFP, hCG and LDH) will be performed prior to the first dose of IP (during the screening period) and within 72 hours prior to IP administration on Day 1 of each cycle of treatment (after Cycle 1) in order to assess response to treatment.

In this patient group, disease progression will be defined as any of the following:

- Two consecutive elevations (i.e. consistent increase between 3 consecutive samples) in any of the three biomarkers.
- Disease progression according to RECIST v1.1, except when pathological evidence of a growing teratoma syndrome is provided.

7.2.8.3 Disease Progression: Special Considerations for NK/T-cell lymphoma

For patients with NK/T-cell lymphoma, in addition to a radiologic disease assessment (FDG-labelled PET-CT scan), PCR analysis of EBV load will be performed prior to the first dose of IP (during the screening period) and then every 84 days (± 7days) in order to assess response to treatment.

DOC43 Protocol ME EN v1.0 05-09-2014

In this patient group, disease progression will be defined as any of the following:

- Disease progression as determined by FDG-PET-CT scan according to the 5-PS.
- A significant increase in the EBV DNA copy number which in the Investigators opinion is indicative of disease progression

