- 18. Any condition which in the Investigator's opinion makes it undesirable for the subject to participate in the trial or which would jeopardize compliance with the protocol.

Protocol n° UC-0105/1612 - version n°10.0. November 22, 2021

PRIMARY ENDPOINT:

Objective response rate (ORR) per cohort, defined as the percentage of patients in each cohort with a complete response (CR) or partial response (PR), measured at the first scheduled disease assessment following study treatment initiation (Day 84, ± 7 days) as assessed by an IRC according to; (i) RECIST v1.1 for patients with solid tumours, (ii) RECIST v1.1 combined with biomarker assessment for patients with germ-cell cancer, (iii) IPCG response criteria for patients with PCNSL, (iv) the 'Lugano' criteria for response assessment using the FDG-PET-CT 5-PS and assessment of EBV load for patients with NK/T-cell lymphoma

Patients who withdraw from the study prior to this time point and patients with non-evaluable disease will be considered as 'non-responders'.

SECONDARY ENDPOINT(S):

- Progression-free survival, defined as the time from inclusion until documented disease progression (PD) according to RECIST v1.1, or RECIST v1.1 combined with biomarker assessment, or IPCG response criteria, or Lugano 5-PS criteria, or death, whichever occurs first.
- Overall survival, defined as the time from inclusion until death due to any cause.
- Best response to treatment according to RECIST v1.1, or RECIST v1.1 combined with biomarker assessment, or IPCG response criteria, or Lugano 5-PS criteria, measured at any disease assessment during the course of the study.
- Response duration, defined as the time from first observation of objective response (i.e. PR or CR) according to RECIST v.1.1, or RECIST v1.1 combined with biomarker assessment, or IPCG response criteria, or Lugano 5-PS criteria, until PD or death, whichever occurs first.
- Time to response, defined as the time from inclusion until observation of objective response (i.e. PR or CR) according to RECIST v1.1, or RECIST v1.1 combined with biomarker assessment, or IPCG response criteria, or Lugano 5-PS criteria, during the course of the study.
- Frequency and severity of adverse events assessed according to the NCI CTCAE v4.

D) INVESTIGATIONAL MEDICINAL PRODUCTS

PRODUCT NAMES AND ADMINISTRATION:

Drug name (INN)	Registered name	Pharmaceutical form	Administration route	Posology

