The first stage treats all patients from the different cohorts with the investigational product and identifies possibly sensitive subpopulations (Berry 2013). The second stage will compare response rates across subsets within the selected cohorts (Trippa 2012).

The first stage will analyse data in each cohort independently of each other. Interim analysis of the ORR according to investigators' assessment is planned after 10 first patients eligible enrolled in the cohort have completed the first scheduled disease evaluation. Based on the estimated response rate and its posterior distribution in each cohort, cohorts that do not reach a minimal ORR of 0.1 (85% confidence) will be potentially closed to further recruitment. In addition, individual cohorts may also be closed during stage 1 if a minimal level of accrual (10 patients in the 2 years after activation of the first site) is not achieved.

In the second stage, intra-cohort analyses will be performed after every 5 additional patients accrued (Berry 2013). These analyses will use all data accumulated up to that point, and will consider potential predictive markers of efficacy; such subset analyses will result in potentially sub-cohorts of poor outcomes that may be proposed for enrolment discontinuation while those of good outcomes will enrich the design (Mandrekar 2009; Zang 2016). In the absence of a decision to halt enrolment, accrual in each cohort will continue until the end of the planned recruitment period (3 years after activation of the first site) or a maximal size by cohort of 50 patients (whatever occurs first) except for the cohorts that were amended where the maximal number of patients may be increased.

Final analysis of efficacy endpoints will be performed using both the Investigator and IRC assessment of response according to: (i) RECIST v1.1, (ii) RECIST v1.1 combined with biomarker assessment (iii) IPCG response criteria, or (iv) Lugano 5-PS criteria. Comparisons between Investigator and IRC results will also be reported. Point estimates will be provided with 95% confidence intervals. Predictive analyses of response will be performed.

All analyses will be performed for the primary cohort and the Re-challenge cohort, separately.

F) SAMPLES COLLECTED FOR TRANSLATIONAL RESEARCH

SAMPLE TYPES:

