- (19) Appropriate biological assessments to be performed at the Investigator's discretion.
- (20) For patients with germ-cell cancer only: measurements of alpha-fetoprotein (AFP) and human chorionic gonadotropin (hCG) and lactate dehydrogenase (LDH) will be performed prior to the first dose of IP (during the screening period) and within 72 hours prior to IP administration on Day 1 of each cycle of treatment (after Cycle 1).
- (21) Disease response in solid tumours to be assessed according to RECIST v1.1 (Appendix 1) (including documentation of size/status of each measurable and non-measurable lesion). For patients with germ-cell cancer response will be assessed using RECIST v1.1 combined with biomarker assessment (AFP, hCG, LDH, Appendix 2).
- (22) Gadolinium-enhanced MRI may be substituted with contrast-enhanced CT scans in patients for whom MRI is medically contraindicated
- (23) Detailed ophthalmologic examination including: dilated fundus examination, slit-lamp examination and colour photography of the posterior pole.
- (24) Tests that were negative at screening do not have to be repeated unless clinically indicated by new symptoms.
- (25) For patients with PCNSL response assessment is to be made according to IPCG response criteria (Appendix 3).
- (26) For patients with NK/T-cell lymphoma response assessment is to be made according to the Lugano 5-point scale response criteria (Appendix 4)
- (27) Verification of availability of a suitable FFPE biopsy sample of a metastatic site, or primitive tumour tissue. If suitable archived biopsy material is not available, a fresh biopsy of a tumour lesion may be performed following signature of the informed consent form and prior to the first administration of IP, unless this is medically contraindicated.
- (28) Blood samples to be collected prior to the first dose of IP (during the screening period) and following IP administration on C1D1, C2D1, C3D1 & C4D1 and when an immune related toxicity event is suspected.
- (29) This information may be collected during onsite visits (as part of patients continued treatment at the site), via communication with the patients treating physician or via telephone contact with the patient.

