3.1.2 Secondary Endpoint(s)

- Progression-free survival, defined as the time from inclusion until documented disease progression (PD) according to RECIST v1.1, or RECIST v1.1 combined with biomarker assessment, or IPCG response criteria, or Lugano 5-PS criteria, or death, whichever occurs first.
- Overall survival, defined as the time from inclusion until death due to any cause.
- Best response to treatment according to RECIST v1.1, or RECIST v1.1 combined with biomarker assessment or IPCG response criteria, or Lugano 5-PS criteria, measured at any disease assessment during the course of the study.
- Response duration, defined as the time from first observation of objective response (i.e. PR or CR) according to RECIST v.1.1, or RECIST v1.1 combined with biomarker assessment, or IPCG response criteria, or Lugano 5-PS criteria, until PD or death, whichever occurs first.
- Time to response, defined as the time from inclusion until observation of objective response (i.e. PR or CR) according to RECIST v1.1, or RECIST v1.1 combined with biomarker assessment, or IPCG response criteria or Lugano 5-PS criteria, during the course of the study.
- Frequency and severity of adverse events assessed according to the National Cancer Institute (NCI) Common terminology criteria for adverse events, version 4 (CTCAE v4, Appendix 5).

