In the absence of a decision to halt enrolment, accrual in each cohort will continue until the end of the planned of recruitment period (3 years after activation of the first site) or a maximal accrual of 50 patients is achieved (whatever occurs first). In case of promising subtypes, enrolment could increase possibly above the pre-established limit of 50 patients, unless the maximal sample size of 350 patients has been reached or the termination date of study enrolment. There is no drawback from a statistical point of view that sample size of cohorts will differ from one another, while increased subsamples may allow more accurate estimates of the outcome in those subsets.

Note: Patient enrolment will be suspended for each cohort following the inclusion of the 10 first patients eligible until the outcome of the interim analysis is known. Enrolment may be reopened prior to the interim analysis upon the decision of the Steering Committee if there is a recognised clinical need and provided that at least one response has been observed and confirmed by a collegiate revue.

Rare ovarian cancer cohort: due to the aggressively of this disease and the prognostic heterogeneity between ovarian cancer subtypes with the difficulties this poses in the interpretation of response rate, the decision to continue enrolment in this cohort will also take into account the number of patients with stabilisation of their disease. Recruitment to this cohort will continue (up to 50 patients) if $\geq 4/10$ patients achieve at least stable disease at their first disease evaluation. Response rate will be subsequently reevaluated for each histological subset following the inclusion of the 10 first patients of each type with the application of the stopping rule as outlined below. In the subset of promising subtypes (teratoma and low-grade serous carcinoma), enrolment will increase possibly above the pre-established limit of 50 patients.

Final analysis of efficacy endpoints will be performed using both the Investigator and IRC assessment of response according to RECIST v1.1, or RECIST v1.1 combined with biomarker assessment, or IPCG response criteria, or the 'Lugano' response using the FDG-PET-CT 5-PS and assessment of EBV load. Comparisons between Investigator and IRC results will also be reported.

Statistical data will be expressed in the form of:

- Frequencies and Percentages (qualitative variables),
- Mean and standard deviation

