⁶ Barrington SF, Mikhaeel NG, Kostakoglu L, Meignan M, Hutchings M, *et al.* Role of imaging in the staging and response assessment of lymphoma: Consensus of the International Conference on Malignant Lymphomas Imaging Working Group. *JCO*. 2014; 32(27):3048-3058

Page 100 / 105

Response	Site	Criteria
Progressive disease (any)	Individual target nodes/nodal	Score 4 or 5 with an increase in intensity of uptake from baseline and/or
masses, extranodal lesions		New FDG-avid foci consistent with lymphoma at interim or end-of-treatment assessment
	New lesions	New FDG-avid foci consistent with lymphoma rather than another etiology (eg, infection, inflammation). If uncertain regarding etiology of new lesions, biopsy or interval scan may be considered
	Bone marrow	New or recurrent FDG-avid foci

5PS= 5-point scale; CT= computed tomography; FDG= fluorodeoxyglucose; PET, positron emission tomography

†PET 5PS: 1, no uptake above background; 2, uptake ≤ mediastinum; 3, uptake > mediastinum but ≤ liver; 4, uptake moderately > liver; 5, uptake markedly higher than liver and/or new lesions; X, new areas of uptake unlikely to be related to lymphoma.

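### Cohort 7 (NK/T-cell lymphoma): an investigator-judged EBV-DNA rise alone is progression in Section 7.2.8.3, while PFS and response duration are defined by PET-based Lugano 5-PS, and the protocol does not say which governs

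*Protocol*

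**What the plan says.** **Progression rule.** Section 7.2.8.3 lists two criteria for Cohort 7, either of which is enough: progression on FDG-PET-CT by the 5-point scale, or "A significant increase in the EBV DNA copy number which in the Investigators opinion is indicative of disease progression".

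**Endpoint definitions.** Section 3.1.2 ties PFS for this cohort to Lugano: "IPCG response criteria, or Lugano 5-PS criteria, or death, whichever occurs first". The synopsis agrees ("or Lugano 5-PS criteria, or death, whichever occurs first"), and response duration uses the same list of criteria. Appendix 4 defines progressive disease only by FDG findings: "Score 4 or 5 with an increase in intensity of uptake from baseline and/or" new FDG-avid foci. Flow-chart footnote 26 also names Lugano alone: "For patients with NK/T-cell lymphoma response assessment is to be made according to the Lugano 5-point scale response criteria".

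**Analysis text.** For the final efficacy analysis, Section 10.2 describes the Lugano "response using the FDG-PET-CT 5-PS and assessment of EBV load". The synopsis describes the same analysis with "iii) IPCG response criteria, or (iv) Lugano 5-PS criteria" and no EBV. The primary endpoint (3.1.1, 10.2.1) and the re-challenge criteria (5.5) also mention EBV load. Section 6.1 uses EBV to sub-classify complete responders.

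**Imaging after treatment stops.** Sections 6.1, 7.3.1 and 7.4.2 continue 84-day disease evaluation only for patients who stopped for a reason other than progression (death and consent withdrawal aside).

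**EBV sampling.** Sections 7.2.8 and 7.2.8.3 put EBV PCR at the 84-day evaluation. In the flow chart, EBV PCR at CnD1 carries a plain X, without the 84-day footnote (14) attached to the other NK/T-cell evaluations in that column.

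**The concern.** A time-to-event endpoint needs one event definition. Here the section that instructs sites has a criterion that the endpoint section and the response appendix lack, and that criterion rests on opinion in an open-label study. The final analysis reports both investigator and IRC assessments. The IRC may be given the EBV values (6.1.1), but it has no stated rule to apply to them.

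Follow-up depends on the same word. If a site records an EBV-only rise as progression, serial PET may stop. An SAP can choose the event rule later, but it cannot recover scans that were never done. At stake are the event status and dates behind Cohort 7 PFS and response duration.

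**Working it through.** There is no planned figure to reproduce, so the check is mainly textual.

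**Step 1: one patient, two rules.** Take a Cohort 7 patient whose PET shows no rise in uptake and no new foci, but whose EBV DNA rises and is judged by the investigator to show progression.

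| Section applied | Progression? | PFS and response duration |
|---|---|---|
| 7.2.8.3 | Yes | Event; response ends on that date |
| 3.1.2 with Appendix 4 | No | No event; response continues |
| 10.2 | Not determined | EBV load is named, but no progression rule is given |

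**Step 2: comparison with germ-cell cancer.** There the marker counts and the text is consistent. Section 3.1.2 names biomarker assessment, and 7.2.8.2 and Appendix 2 give the same objective rule: "Two consecutive elevations (i.e. consistent increase between 3 consecutive samples) in any of the three biomarkers". Cohort 7 has no equivalent in 3.1.2 or Appendix 4.

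**Step 3: what each combination of readings does.**

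| Sites | Analysis | Result |
|---|---|---|
| PET only | PET only | Serial PET continues; nothing is lost |
| EBV counts | EBV counts | One rule, but EBV-only events rest on opinion without a threshold |
| EBV counts | PET only | Serial PET may stop with no event counted; the patient is censored when judged to be worsening, which is likely informative |

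In the third case, what is lost is the date of any later PET progression. Survival is still collected for 12 months after the end-of-treatment visit (7.4.1), and death is a PFS event.

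**Step 4: the arithmetic that the protocol allows.**
- Scheduled PETs not done in 12 months of follow-up: 365/84 = 4.3, so up to 4 per affected patient.
- Change in the crude event proportion per reclassified patient, assuming the planned 20 to 50 patients: 1/50 = 2 points to 1/20 = 5 points. This is a unit of change and does not estimate bias. The planned summary is Kaplan-Meier (10.2), and a cohort with too little accrual may close early (10.3).
- Time spanned by three consecutive samples: 2 × 21 = 42 days if EBV is drawn each cycle, or 2 × 84 = 168 days on the schedule in 7.2.8.3. The two EBV schedules therefore matter for any confirmation rule.

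**Step 5: PET status at the call.** If EBV is sampled only at the 84-day evaluation, PET is done at the same visit. If it is sampled each cycle, a call can fall between scheduled PETs, and PET status then depends on footnote 14, which also asks for evaluation in case of progression. The documents do not settle which applies.

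**The case against.** The best defence is that the label in 3.1.2 is shorthand. The synopsis and 10.2 describe the same final analysis, one with Lugano 5-PS alone and one with EBV load added, and 3.1.1, directly above 3.1.2, uses the longer form. Section 7.2.8.3 is specific to the cohort and would ordinarily complete a general definition. Appendix 4 reproduces a published PET table, so a trial-specific EBV criterion would not be expected there. On this reading EBV counts and there is only one rule.

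That reading is plausible but not decisive. None of the passages that add EBV load says what EBV change is progression, and 3.1.2 does not refer to 7.2.8.3. If the reading is accepted, events still rest on an opinion without a threshold.

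Three further points stand. Nothing says that the analyst will count PET events only, and censoring rules are commonly left to the SAP, which is not shown. Imaging also ends at new antineoplastic therapy, and every patient has an end-of-treatment disease evaluation (7.3.1), so continued PET may recover little. Finally, a PET-only rule would conflict with 10.2 unless that wording is changed too.

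A reader might infer that Cohort 7 PFS will be biased by informative censoring. The documents do not support this: it needs the mixed case in Step 3, and no frequency of EBV-only calls is given. Nor do they support the inference that 3.1.2 plainly makes PFS PET-only and 7.2.8.3 is simply an error, because 10.2 points the other way.

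**Conclusion.** The inconsistency holds. Event status in Cohort 7 depends on the section followed, the EBV criterion is neither objective nor confirmed, and an EBV-only call can end serial PET. This affects PFS and response duration in one of seven cohorts of a non-randomised study. The primary ORR is unaffected: it is the IRC-read proportion of CR and PR at the first evaluation and does not use the progression rule. The size of the effect is unknown. The loss of PET data assumes that sites treat an EBV-only call as progression when applying the imaging rule; the censoring problem also assumes that the analysis counts PET events only. Severity is minor to moderate.

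**What to change.** State one event rule for Cohort 7 PFS and response duration.

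- **Option A, PET only.** The event is 5-PS progression on PET-CT, or death. EBV rise is reported separately and may remain a reason to stop treatment. Align 7.2.8.3, 3.1.2 and the EBV wording in 10.2.
- **Option B, EBV counts.** Put an objective rule, confirmed on a repeat sample, in 7.2.8.3 and 3.1.2. The repeat should come at the next 21-day visit, because waiting for 84-day samples is too slow.

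Under either option, state in 6.1, 7.3.1 and 7.4.2 that a stop for EBV rise alone counts as a reason other than disease progression. The existing 84-day PET schedule then continues until PET progression, new antineoplastic therapy or death. The same imaging rule recurs in the synopsis, Section 3.2, the introduction to Section 7 and flow-chart footnote 15, and should match. Also reconcile the EBV sampling interval between 7.2.8.3 and the flow chart.

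The cost is wording, plus up to about 4 PETs of the kind already scheduled for each patient stopped for EBV alone. Under Option A, relapses that show first in EBV are dated later. The imaging change helps only patients who have not yet left serial PET; the event rule can still be fixed before the final analysis, planned about 4 years after last enrolment (10.1).

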7.3 End-of-Treatment Visit

Patients will continue to receive study treatment, and undergo study procedures as outlined above for a maximum of 24 months (or 35 cycles, whichever is longer), or until disease progression. Treatment may also be terminated early at the initiative of either the patient or the investigator for any reason that would be beneficial to the patient, including: unacceptable toxicity, intercurrent conditions that preclude continuation of treatment, or patient request.

Following treatment discontinuation for any reason, the following examinations are to be performed $30 (\pm 3)$ days after last dose of IP, or before initiating a new antineoplastic therapy, whichever comes first:

- Complete clinical examination (major body systems)
- Measurement of vital signs (blood pressure, seated heart rate, body temperature)
- Assessment of ECOG performance status
- · Assessment of new and ongoing toxicities.
- Haematology analysis (see Table 5).
- Serum chemistry (see Table 5).
- Thyroid function tests: TSH, T3, T4 (see Table 5).

Note: Laboratory examinations that were performed less than 14 days prior to the EoT visit do not need to be repeated, unless clinically indicated (i.e. ongoing toxicity surveillance).

All AEs that occur prior to the EoT visit should be recorded. Subjects with an AE of Grade > 1 will be followed until the resolution of the AE to Grade 0-1 or until the beginning of a new anti-neoplastic therapy, whichever occurs first. Treatment-related SAEs that occur more than 28 days after the end of treatment or before initiation of a new anti-cancer treatment should also be followed and recorded.

